### **Decimal Places**

Summary statistics of mean, median, and quartiles (location parameters) will be reported to one more decimal place than the collected data. For derived data, the maximum number of decimal places of the variables used in the derivation will determine the number of decimal places of the derived variable. For example, BMI uses 2 collected variables, height in meters (m) and weight in kilograms (kg). If the height is collected in centimeters, height in m will have 2 decimal places. Weight may be collected with 1 decimal place. Thus BMI will be considered to have 2 decimal places on observation level. The SD (parameter for variability) will be reported to one more decimal place than the mean. For example, the mean and median for age will be reported to one decimal place because it is collected in full years. The SD of age will then be reported to 2 decimal places. Descriptive percentages and proportions will be displayed to one decimal place. Duration of AEs will be displayed to 1 decimal place.

### **Formatting for Dates and Times**

- Dates only – ddmmmyyyy;
- Times only – hh:mm or hh:mm:ss (as appropriate);
- Dates and times – ddmmmyyyy hh:mm or ddmmmyyyy hh:mm:ss (as appropriate).

### **Planned and Actual Times in Summaries**

Planned times for study treatment dosing will be used in all tables and summary figures.

Generally, only pre-specified planned times will be used in the summaries, statistical analyses, and calculations of any derived parameters; unscheduled assessments will be included in the listings. However, both unscheduled and scheduled assessments will be included in worst-case post-baseline shift displays for laboratory data and in any summary or listing of potential clinical importance values for vital signs.

The infusion start date and time will be mapped to study weeks in the following way: The infusions will be sorted by start date and time and will be consecutively numbered. The infusions will be mapped to study weeks using the consecutive numbers.

Study Week	Pump-Assisted Cohorts	Manual Push Flow Rate Cohort			
		Infusions Per Week			
		2	3	4	5
1	Infusion 1	Infusion 1-2	Infusion 1-3	Infusion 1-4	Infusion 1-5
2	Infusion 2	Infusion 3-4	Infusion 4-6	Infusion 5-8	Infusion 6-10
3	Infusion 3	Infusion 5-6	Infusion 7-9	Infusion 9-12	Infusion 11-15
4	Infusion 4	Infusion 7-8	Infusion 10-12	Infusion 13-16	Infusion 16-20
5	Infusion 5	Infusion 9-10	Infusion 13-15	Infusion 17-20	Infusion 21-25
...	...				
9	Infusion 9	Infusion 17-18	Infusion 25-27	Infusion 33-36	Infusion 41-45
...	...				
12	Infusion 12	Infusion 23-24	Infusion 34-36	Infusion 45-48	Infusion 56-60
...	...				
16	Infusion 16 (PAFR)				

PAFR: Pump-Assisted Flow Rate Cohort

### 7.1 Multicenter Studies

Data from all participating sites will be pooled prior to analysis. Listings will include site information. The site will not be considered in any analysis.

### 7.2 Treatment Descriptors

For output displayed by cohort the following labels and order will be used:

- Pump-Assisted Volume Cohort;
- Pump-Assisted Flow Rate Cohort;
- Manual Push Flow Rate Cohort;
- Total (optional).

For output displayed by infusion parameters within cohort the following labels and order will be used:

- Pump-Assisted Volume Cohort: 25 mL, 40 mL, 50 mL, Total (optional);
- Pump-Assisted Flow Rate Cohort: 25 mL/h, 50 mL/h, 75 mL/h, 100 mL/h, Total (optional);

- Manual Push Flow Rate Cohort: 30 mL/h [0.5 mL/minute], 60 mL/h [1 mL/minute], 120 mL/h [2 mL/minute], Total (optional).

The display of the output will be specified in the TFL shells document.

### 7.3 Multiple Comparisons and Multiplicity

Type I error rate adjustment is not applicable as there is no confirmatory test planned in this study. **CCI**

## 8 Data Handling Conventions

In the event that the study is terminated, all available data will be listed and a review carried out by the study team to assess which statistical analyses are to be performed.

### 8.1 Missing Data

#### 8.1.1 Imputation of Non-Date Missing Data

Missing data occurs when any requested data is not provided, leading to blank fields on the collection instrument. These data will be indicated by the use of a “blank” in subject listing displays. Answers such as “Not applicable” and “Not evaluable” are not considered to be missing data and should be displayed as such.

Subjects with the designation of treatment relationship for AEs and serious AEs (SAEs) missing will have the worst realistic case assumed to impute the relationship: if relationship to study treatment is missing and the AE started on or after the first infusion of study treatment it will be assumed to be “Related” (worst case). If the AE with missing relationship to treatment started before the first infusion of study treatment, it will be considered as “Not Related” (realistic case). There will be no other imputation for missing data.

For variables which determine the proportion of subjects, all subjects in the SAF will be included in the denominator when calculating the percentages irrespective of whether their outcome may be missing.

#### 8.1.2 Imputation of Partial Dates

A worst-case approach will be used to assign AE flags or concomitant medication flags if start dates of AEs or concomitant medications are missing or partially missing. Details are given in the respective sections. Study day, durations, or other time variables based on dates

cannot be calculated for partially missing start dates and thus will be missing. Except for the calculation of the duration of an AE for which the following approach will be used: For the calculation of the duration of an AE, missing end dates will not be imputed for AEs which are ongoing. For ongoing AEs the end date and thus the duration will not be available by definition. If the outcome of the AE indicates that the AE is resolved but the end date is still completely missing, the data entry date for this information will be used as AE end date. If only the end day is unavailable, the last day of the month or the subject's study end date whatever occurs first will be imputed as AE end date for the calculation of the AE duration. This approach will be followed in order to avoid underestimation of durations of AEs.

Missing infusion end date and time will be imputed by adding the infusion duration to the infusion start date and time.

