2.2.2 Secondary Endpoints

The secondary endpoints are as follows:

- The rate of total AEs per subject and per infusion by cohort and by each of the infusion parameter levels within the cohort.
- The rate of local reactions per subject and per infusion by cohort and by each of the infusion parameter levels within the cohort.
- The time to onset of local reactions per subject and per infusion by cohort and by each of the infusion parameter levels within the cohort.
- Severity of local reactions per subject and per infusion by cohort and by each of the infusion parameter levels within the cohort.
- Duration of local reactions per subject and per infusion by cohort and by each of the infusion parameter levels within the cohort.
- For all cohorts: Tolerability of a certain infusion parameter; ie, percentage of infusions per cohort by volume/flow rate subgroup experiencing no severe local reactions for each of the infusion parameter levels.

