### 8.2.3 Durations

Durations of an event (e.g., the duration of an AE) will be calculated in days as:

- event end date – event start date + 1;

Thus, there will be no duration of 0. If start and end time is available, it will also be used to calculate the duration. For AEs with missing end date, the approach as specified in Section 8.1.2 will be followed.

For elapsed time (e.g., the time since PID diagnosis) use

- event date – reference date.

Thus, an event which happens on the same date as the reference date will have an elapsed time of 0.

To transform durations in days into months, divide the number of days by 30.4375; to report in weeks divide the number of days by 7; to report in years divide the number of days by 365.25. These algorithms return decimal numbers, and ignore the actual calendar days in the months or years between start date and end date.

Age will be calculated as the number of complete years between a subject's birth date and the date of informed consent. If the birth date is incomplete, the subject's birth year will be used to calculate age.

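### Ongoing local reactions drop out of the duration summaries, and date-based and clock-based durations are mixed without a rule; the net direction of the error is unknown

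*SAP*

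**What the plan says.** Protocol 2.2.2 lists as a secondary endpoint: "Duration of local reactions per subject and per infusion by cohort and by each of the infusion parameter levels within the cohort". SAP 11.4 serves it with a table of descriptive statistics and the categories 1 day, 2 days, 3 days and > 3 days. Local reactions enter that table through a virtual system organ class.

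SAP 8.1.2 sets three rules for AE end dates.
- Ongoing events: "missing end dates will not be imputed for AEs which are ongoing", with the consequence "For ongoing AEs the end date and thus the duration will not be available by definition".
- Resolved events with no end date at all: "the data entry date for this information will be used as AE end date".
- Missing day only: "If only the end day is unavailable, the last day of the month" is used, or the subject's study end date if that comes first.

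The paragraph closes on its purpose: "This approach will be followed in order to avoid underestimation of durations of AEs".

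SAP 8.2.3 defines duration in days as "event end date – event start date + 1" and rules out a value of zero. It then adds: "If start and end time is available, it will also be used to calculate the duration". The definitions table in SAP 2.2 gives the date formula only. SAP 7 displays AE durations to one decimal place, shows missing categorical values as a separate category, and bases percentages on non-missing values.

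Protocol 9.5.1 and 9.9 require an AE that is ongoing at End of Study to be followed until it resolves or stabilises, or the subject is lost to follow-up.

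**The concern.** There are two separate problems.

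First, an event that is still ongoing has a known minimum duration, and the planned summaries do not use it. Long events are the likeliest to be unresolved at last contact, so leaving them out removes the long end of the distribution. The endpoint exists to show whether reactions last longer at higher volumes or flow rates. For a subject who titrates fully, the last level is also the top level and has the least follow-up before End of Study, so the loss could fall unevenly across the levels being compared.

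Second, the same reaction can receive different durations depending only on whether clock times were entered. If completeness of times differs between levels, a trend across levels could be created or hidden. Two programmers could also produce different tables from the same data.

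**Working it through.** The documents give no figure for AE duration, so there is nothing to reproduce. Reaction lengths and ongoing shares below are assumptions.

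**1. A known-long event that is not counted.** In the 12-week cohorts the Week 12 infusion is on Day 78 and End of Study is on Day 85 (Protocol 8.4.3.6 and 8.4.4). A reaction that starts on Day 78 and is unresolved on Day 85 has lasted at least 85 − 78 + 1 = 8 days by the SAP's formula. It belongs in > 3 days. If it never receives an end date, it has no duration and enters no category percentage.

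**2. Follow-up by level.** For weekly infusions in the volume cohort, the last infusion at the middle level (Day 50) is followed by 85 − 50 = 35 days to End of Study. The last infusion at the top level is followed by 85 − 78 = 7 days.

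**3. Possible shortening at the last level.** Assume a reaction starts at an infusion, has exponential duration with mean m, and gets no end date after End of Study. For weekly pump infusions the times to End of Study are c = 28, 21, 14 and 7 days. For daily manual push they are 28, 27, …, 1.

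- Share ongoing = average of exp(−c/m).
- Mean of completed events = Σ[m(1 − exp(−c/m)) − c·exp(−c/m)] / Σ[1 − exp(−c/m)].

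For weekly pump with m = 5, the values of exp(−c/m) are 0.0037, 0.0150, 0.0608 and 0.2466, so 8.2% are ongoing. The completed mean is (4.878 + 4.610 + 3.845 + 2.041)/3.674 = 15.374/3.674 = 4.18 days, which is 16% below 5.

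| True mean (days) | Weekly pump: ongoing | Completed mean | Fall | Daily push: ongoing | Completed mean | Fall |
|---|---|---|---|---|---|---|
| 1 | 0.0% | 1.00 | 0% | 2.1% | 0.97 | 3% |
| 2 | 0.8% | 1.94 | 3% | 5.5% | 1.85 | 7% |
| 3 | 2.7% | 2.79 | 7% | 9.0% | 2.65 | 12% |
| 5 | 8.2% | 4.18 | 16% | 16.1% | 3.96 | 21% |
| 7 | 14.3% | 5.24 | 25% | 22.8% | 4.93 | 30% |

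Under the exponential assumption these are upper bounds, because the protocol requires follow-up past End of Study.

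**4. Rules that act the other way.** With onset uniform over the day and true length D days, the date rule gives floor(U + D) + 1, where U is the time of onset as a fraction of a day. Its mean is D + 1, so it exceeds elapsed time by 1.0 day on average. Month-end imputation also lengthens: a 2-day event starting on a random day of a 30-day month is recorded at (30 + 29 + … + 2 + 31)/30 = 495/30 = 16.5 days on average, before the study-end cap. The data entry date likewise tends to fall after the true end.

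**5. Net effect.** Suppose completed events average 2 days elapsed and all use the date rule, so the reported mean is 3.
- 5% ongoing, lasting 10 days: true mean 0.95 × 2 + 0.05 × 10 = 2.4, so the report is 0.6 day too long.
- 10% ongoing, lasting 20 days: true mean 0.90 × 2 + 0.10 × 20 = 3.8, so the report is 0.8 day too short.

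The sign depends on inputs that the documents do not give.

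**6. Scale.** A reaction from 22:00 to 02:00 is 2 days by dates. By clock it is 4/24 = 0.17, shown as 0.2; by clock with the + 1 kept it is 1.2. For 6-hour reactions, if the + 1 is dropped when times exist, the mean runs from 0.25 day (all timed) to 1.25 days (none timed). If the + 1 is kept, the average is 1.25 either way, though individual values still differ. The only rounding rule in SAP 11.4 follows the time-to-onset formula. Applied to duration it would turn 0.2 into 0, which is not a duration category.

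**The case against.** A reader might infer that the endpoint as a whole is biased downward. The documents do not support that. The + 1 rule, the data entry date and month-end imputation generally lengthen durations, and mixing scales causes inconsistency rather than shortening. The lengthening has one exception: when the missing end day belongs to a resolution after study end, the cap places the end too early.

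Nor is it established that the shortening is in fact largest at the top level. Follow-up continues after End of Study, so only events that never resolve, that stabilise without an end date, or that are lost to follow-up should stay without a duration. This objection stands. It reduces the loss but does not remove it.

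It can also be said that ongoing events are not hidden. They count in the incidence and severity tables, they are listed, and a missing category may show them. That is correct, but a count of missing values corrects neither the mean and median nor the > 3 days percentage.

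The sentence on avoiding underestimation directly follows the two imputation rules and can be read as covering only those. It is therefore safer to say that the aim is not carried through to ongoing events than that the SAP contradicts itself.

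Finally, SAP 8.2 leaves full derivation details to separate dataset specifications, which may settle the + 1 question. The SAP text itself leaves it open.

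**Conclusion.** The point holds in a limited form. Ongoing local reactions leave the duration statistics and category percentages even when already known to exceed 3 days. This component can only act towards shorter durations, and would tend to do so most at the last level tested. Under the stated assumptions it is negligible to small for reactions averaging 1–2 days and reaches 16–30% of the mean for 5–7 days, before allowing for follow-up after End of Study. The net direction across all rules is unknown.

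Separately, the duration scale is undefined where clock times exist. The average gap between scales is 1.0 day if the + 1 is dropped for timed events, which is large beside categories one day wide.

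The endpoint is descriptive and untested. It plays no part in the 33% success criterion or the label rule in SAP 11.1, so this is a low-cost improvement to the reporting of local tolerability.

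**What to change.** Amend SAP 8.1.2, 8.2.3 and 11.4 as follows.
- Count an ongoing event already observed for more than 3 days in the > 3 days category.
- Report the number of ongoing events per infusion parameter level beside each duration summary, separate from other missing durations.
- Add an event-level Kaplan-Meier median and quartiles, with ongoing events censored at last follow-up.
- Use one scale for all events in the main table. Whole days by the + 1 rule fits the existing categories. Show hours separately for events with both times recorded.

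No new data collection is needed. The cost is a few sentences in the SAP and slightly more analysis and programming. The Kaplan-Meier summary ignores clustering of reactions within subjects, so it should be labelled descriptive and given no inferential weight. Whole days by the + 1 rule will still record a 4-hour reaction across midnight as 2 days, which is why the hours display is worth keeping alongside.

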9.5 Adverse Event Reporting

9.5.1 Adverse Events

At each clinical evaluation, the investigator (or delegate) will determine whether any AEs have occurred. AEs will be recorded in the AE page of the eCRF. If known, the medical diagnosis of an AE should be recorded in preference to the listing of individual signs and symptoms. The investigator must follow up on the course of an AE until resolution or stabilization. If an AE is ongoing after the End of Study visit, the AE will continue to be followed up until resolution, stabilization, or the subject is lost to follow-up. Subjects who drop out of the study due to reasons other than ‘consent withdrawn’ or ‘lost to follow-up’ will be followed up by weekly telephone calls by site personnel for the full duration of their planned study participation, in order to collect information on AEs.

If, during the study period, a subject presents with a preexisting condition that was not noted at the time of study entry, the condition should be retrospectively recorded in the Medical History section of the eCRF.

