
 
• To evaluate the safety of pump-assisted IgPro20 infusions at higher infusion parameters (volume and flow rate).
 
• To evaluate the safety of manual push IgPro20 infusions.
 
• To evaluate the tolerability of higher infusion parameters of IgPro20.
 
	
 
• The rate of total adverse events (AEs) per subject and per infusion by cohort and by each of the infusion parameter levels within the cohort.
 
• The rate of local reactions per subject and per infusion by cohort and by each of the infusion parameter levels within the cohort.
 
• The time to onset of local reactions per subject and per infusion by cohort and by each of the infusion parameter levels within the cohort.
 
• Severity of local reactions per subject and per infusion by cohort and by each of the infusion parameter levels within the cohort.
 
• Duration of local reactions per subject and per infusion by cohort and by each of the infusion parameter levels within the cohort.
 
• For all cohorts: Tolerability of a certain infusion parameter, i.e. percentage of infusions per cohort by volume/flow rate subgroup experiencing no severe local reactions for each of the infusion parameter levels.
 

Objectives	Endpoints
Exploratory	

 
CCI [REDACTED]
 
[REDACTED]
 
[REDACTED]
 
[REDACTED]
 
	
 
CCI [REDACTED]
 
[REDACTED]
 
[REDACTED]
 

[figure not shown]

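### SAP 8.1.2 caps an AE end date with only the day missing at study end, even when the recorded end month is later, so the imputed duration falls below its possible minimum

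*SAP*

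**What the plan says.** SAP 8.1.2 has three rules for AE end dates that are not complete.

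- **Ongoing AE:** "missing end dates will not be imputed for AEs which are ongoing", so no duration is available.
- **Resolved AE, end date wholly missing:** "the data entry date for this information will be used as AE end date".
- **Only the day missing:** the SAP takes month end or the subject's "study end date whatever occurs first will be imputed as AE end date for the calculation of the AE duration".

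It then gives the purpose: "This approach will be followed in order to avoid underestimation of durations of AEs".

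For complete dates, SAP 8.2.3 defines duration as end date minus start date plus 1, with no limit at study end.

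Protocol 9.5.1 states: "If an AE is ongoing after the End of Study visit, the AE will continue to be followed up until resolution, stabilization", or until the subject is lost to follow-up. Protocol 9.9 repeats this and requires follow-up information to be entered in the eCRF.

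The endpoint that uses these durations is in SAP 4.2 (Protocol 2.2.2): "Duration of local reactions per subject and per infusion by cohort and by each of the infusion parameter levels within the cohort". SAP 11.4 shows duration with descriptive statistics and the categories 1, 2, 3 and more than 3 days.

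**The concern.** The day-missing rule has no exception for an end month that is known to be later than study end. Follow-up past End of Study makes such records foreseeable, and a resolution date learned at a later contact may well lack the exact day. In that case the imputed date is not a cautious guess within the recorded month. It lies outside that month, on the early side.

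A milder form arises when the end month is the study-end month but the AE is known to have been ongoing at the End of Study visit. The imputed end is then the day of a visit at which the event had not ended.

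At stake is the duration of local reactions by infusion parameter level. Titration is upward, so the top level occupies the last four weeks before End of Study. AEs are assigned to the level at which they occur. Shortening of events that outlast study end could therefore make the highest level look slightly better on this endpoint.

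**Working it through.** The plan states no figure to reproduce here. The check applies the rule to dates. Calendar dates are illustrative.

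**Formulas**

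- Rule (SAP 8.1.2): imputed end = the earlier of the last day of the recorded end month and the study end date.
- Duration (SAP 8.2.3): end − start + 1.
- Shortest duration the record allows: end on the first day of the recorded month.
- Longest: end on the last day of that month.

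**Main example.** Onset 3 July, study end 10 July, end 'unknown August'.

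- Rule: the earlier of 31 August and 10 July is 10 July. Duration 10 − 3 + 1 = 8 days.
- Shortest possible: 3 July to 1 August is 29 + 1 = 30 days.
- Longest possible: 3 July to 31 August is 59 + 1 = 60 days.
- Shortfall: at least 30 − 8 = 22 days, at most 60 − 8 = 52 days.

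**The SAP's rules compared on that event**

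| End date on file | Duration |
|---|---|
| Complete, 1 August | 30 days |
| Day missing, August | 8 days |
| Wholly missing, resolved, data entered in August | at least 30 days |

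The record with least information gets a longer duration than the record whose month is known.

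**Other study end dates.** Onset 7 days before study end, AE ended in June, day unknown:

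| Study end | Rule | Possible range |
|---|---|---|
| 10 May | 8 days | 30–59 days |
| 20 May | 8 days | 20–49 days |
| 28 May | 8 days | 12–41 days |
| 31 May | 8 days | 9–38 days |

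With study end on each day of one calendar year in turn, and the AE ending in the next calendar month, the capped value is 1 to 31 days (mean 15.7) below the shortest possible duration. It is 28 to 61 days (mean 45.1) below the value from month end without the cap.

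**Same-month case.** Onset 3 June, study end 10 June, end 'unknown June'. The rule gives 8 days. If the AE is known to have been still ongoing after 10 June, the end lies between 11 and 30 June, which is 9 to 28 days. If it is known to have ended by 10 June, 8 days is the longest possible value and the cap is right.

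**Effect on the categories.** The capped duration is study end − onset + 1. It is 3 days or less only when onset is within 2 days of study end. Example: onset 27 May, study end 28 May, end 'unknown June'. The rule gives 2 days, the possible range is 6 to 35, and the event moves from the more-than-3-days category to the 2-day category. With earlier onset the event stays above 3 days, and only statistics such as the mean, upper quartile and maximum can change.

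**The case against.** The best defence is that the cap is a data cut-off. SAP section 7 uses each subject's data up to the latest of study completion, loss to follow-up or withdrawal, and Protocol 9.4 closes the AE observation period at the End of Study visit. For an AE known to have ended by study end, the earlier of month end and study end is also the latest possible date, so there the rule does what it claims. That part stands, and the cap should be kept for those records.

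The cut-off argument does not cover the rest. Complete end dates and wholly missing end dates are not cut at study end. If data really stopped there, an AE still present would be ongoing and, under the SAP's own rule, would have no duration at all. SAP 8.2 leaves full derivation details to a separate specification that is not among the documents. It may treat this case, but the SAP text as it stands does not.

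The impact is also limited. Safety is descriptive, no confirmatory test is planned, and the label recommendation depends on the responder rate. All of that stands.

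Two stronger readings are tempting and not supported:

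- **An end date before the start date.** A reader might infer negative durations for dropouts whose AE begins after an early End of Study visit. SAP 11.4 keeps only treatment-emergent AEs occurring until that visit in the summary tables, so at most a listing value is affected. The inference also assumes that the study end date of such a subject is the early visit.
- **A fixed ceiling of 8 days at the top level against 31 days at lower levels.** The 8 days come from the nominal schedule (85 − 78 + 1, or 113 − 106 + 1). The ±1-day windows allow 86 − 77 + 1 = 10 days, and manual push infusions can fall later in Week 12. At a lower level 31 days is no maximum: onset 1 July as Day 22, with end 'unknown August', is imputed to 31 August, which is 62 days and still before Day 85.

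**Conclusion.** The rule is wrong as written for one kind of record: a resolved AE with only the end day missing whose end month is after the study-end month, or which is known to have continued past End of Study. In the first case the imputed date contradicts the recorded month, and the duration is 1 to 31 days below its possible minimum when the end falls in the next month. In the second the contradiction is with the AE's known status, and the minimum shortfall is small. Both run against the stated aim.

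The descriptive statistics for duration of local reactions are affected. The categories change only for onset within about 2 days of End of Study.

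A reader might go further and conclude that the comparison between levels is materially biased towards the top level. The documents support only a probable direction. The top level comes last, half of the subjects are assumed to respond there, and AEs of non-responders after non-response are analysed separately. But an early withdrawal can meet the cap at any level, and a long AE may have begun at an earlier one. No document gives the number of affected events, and it is probably small.

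**What to change.** Replace the day-missing sentence in SAP 8.1.2 with a rule to this effect: if only the end day is missing, impute the earlier of month end and study end when the end month is not later than the study-end month and the AE is not known to have continued past study end; otherwise impute the last day of the recorded end month; in no case impute a date before the AE start date.

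This keeps the cap where it is valid. It needs only the recorded month, the study end date, the AE start date and the AE's status at End of Study. If that status is not held as a variable, the month comparison alone still removes every case in which the imputed date contradicts the recorded month.

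The cost is one SAP sentence and a small change to the derivation. A few durations become longer. Month-end imputation can overstate a duration by up to 30 days (31 − 1), which fits the SAP's stated preference for not underestimating.
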